6.2.11 Inexact Values

In the case where a variable is recorded as “> x”, “ $\geq x$ ”, “ $< x$ ” or “ $\leq x$ ”, a value of x will be taken for analysis purposes.

6.2.12 Vital Signs

QMD Ref: Worldwide-TMP-ST-005-7.0 Effective: 12Aug2019	Governing QMD: Worldwide-SOP-ST-001
Confidentiality Statement	

This document is the property of Worldwide Clinical Trials Inc. and may not be duplicated, copied, altered or removed from company without prior approval from Worldwide Quality Assurance or in compliance with Worldwide Standard Operating Procedures.

Worldwide Clinical Trials Controlled Quality Management Document			
 WORLDWIDE CLINICAL TRIALS	Sponsor:	Helixmith Co., Ltd.	
	Protocol Number:	VMALS-002-2b	
STATISTICAL ANALYSIS PLAN. PHASE 2-3-4			

Body Mass Index (BMI) will be calculated as [weight in °KG] ÷ ([height in °CM] ÷ 100)².

6.2.13 Unscheduled Visits

Only scheduled post-baseline values will be tabulated. Post-baseline repeat / unscheduled assessments will not be tabulated, although these post-baseline assessments will be listed in the relevant appendices to the CSR. In all tables, excepting the table for participant visits (Table 14.1.1.2) data of the Early Termination visit will be combined with data of Day 365 visit.

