3. **Complete Physical Examination** will be performed on Days 240 and 365/ET. The examination will include the following: an examination of the skin/integumentary systems, general appearance, head, neck (including thyroid), eyes, ears, nose, throat, lymph nodes, chest (lungs), heart, abdomen, musculoskeletal system, neurological system, and any additional assessments needed to establish Baseline status or evaluate symptoms or TEAEs. Any abnormalities should be categorized as clinically significant (CS) or not clinically significant (NCS), and the abnormalities should be recorded as TEAEs, TESAEs, or AESIs.
4. **12-Lead Electrocardiogram (ECG)** will be performed at Days 240 and 365/ET. Clinically significant abnormalities are to be recorded as adverse events. The ECG recording must be stored with the Participant's records.
5. **Serum Chemistry and Hematology:** Blood samples will be collected for serum chemistry and hematology assessments on Days 240 and 365/ET. Test results will be reviewed and assessed by the Investigator for clinically significant abnormal laboratory findings, which should be recorded as TEAEs, TESAEs, and AESIs.
Chemistry includes sodium, potassium, chloride, bicarbonate, calcium, inorganic phosphate, magnesium, glucose, amylase, lipase, creatine kinase, lactate dehydrogenase, and:
 - a. Kidney function tests (blood urea nitrogen, creatinine)
 - b. Liver function tests (aspartate aminotransferase [AST], alanine aminotransferase [ALT], alkaline phosphatase, gamma-glutamyl transpeptidase [GGT], total bilirubin, total protein, and albumin)**Hematology** includes platelet count, hemoglobin, hematocrit, white blood cell count, and neutrophil count
6. **Concomitant Medications and Procedures** will be recorded on Days 240, 300, and 365/ET, and will include all medications or vaccines, including over-the-counter or prescription medicines, vitamins, herbal supplements, and procedures that the Participant was received. For each medication, treatment, or procedure, the following information will be collected: Medication trade or generic name, type of procedure, indication, start date, stop date or ongoing, dose, units, frequency, and route of administration.
7. **Urine Pregnancy Test** will be conducted for women of childbearing potential on Day 365/ET.
8. **Slow Vital Capacity (SVC)** will be measured on Days 240, 300, and 365/ET.

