8.1.4. Clinical Laboratory Assessments

The Investigator must review the Participant's laboratory test results reports, document this review, and record any clinically relevant changes occurring during the study. The laboratory reports must be filed with the source documents. Clinically significant abnormal laboratory findings are those that are not associated with the underlying disease, unless judged by the Investigator to be more severe than expected for the Participant's condition. Clinically significant abnormal laboratory findings should be recorded as TEAEs, TESAEs, or AESIs using an appropriate medical diagnosis.

Blood sample for laboratory assessments will be collected on Days 240 and 365/ET.

All protocol-required laboratory assessments must be performed in accordance with the laboratory manual and the SoA. The laboratory reports must be filed with the source documents.

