- Alternative causes, such as underlying disease(s), concomitant therapy, and other risk factors, as well as the temporal relationship of the event to study intervention administration will be considered and investigated.
- The Investigator will also consult the IB and/or Product Information, for marketed products, in his/her assessment.
- For each TEAE/TESAE, the Investigator **must** document in the medical notes that he/she has reviewed the TEAE/TESAE and has provided an assessment of causality.
- Situations may arise in which a TESAE has occurred, and the Investigator has minimal information to include in the initial report to the Sponsor or designee. However, the Investigator must always assess causality for every event before the initial transmission of the TESAE data to the Sponsor or designee. Death or hospitalization are not to be specified as a TESAE; these are criteria to determine seriousness.
- The Investigator may change his/her opinion of causality in light of follow-up information and send an TESAE follow-up report with the updated causality assessment.
- The causality assessment is one of the criteria used when determining regulatory reporting requirements.

Follow-up of TEAEs and TESAEs

- The Investigator is obligated to perform or arrange for the conduct of supplemental measurements and/or evaluations as medically indicated or as requested by the Sponsor or designee to elucidate the nature and/or causality of the TEAE or TESAE as fully as possible. This may include additional laboratory tests or investigations, histopathological examinations, or consultation with other health care professionals. New or updated information will be recorded in the originally completed eCRF.
- The Investigator will submit any updated TESAE data to the Sponsor or designee within 24 hours of receipt of the information.

10.2.5. Reporting of TESAEs**TESAE Reporting to the Sponsor or Designee via an Electronic Data Collection Tool**

- The primary mechanism for reporting an TESAE to the Sponsor or designee will be the eCRF.
- The Site will enter the TESAE data into the electronic system as soon as it becomes available.
- After the study is completed at a given Site, the electronic data collection tool will be taken off-line to prevent the entry of new data or changes to existing data.

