3 ENDPOINTS

3.1 Primary Endpoints

QMD Ref: Worldwide-TMP-ST-005-7.0 Effective: 12Aug2019	Governing QMD: Worldwide-SOP-ST-001
Confidentiality Statement	

This document is the property of Worldwide Clinical Trials Inc. and may not be duplicated, copied, altered or removed from company without prior approval from Worldwide Quality Assurance or in compliance with Worldwide Standard Operating Procedures.

Worldwide Clinical Trials Controlled Quality Management Document			
 WORLDWIDE CLINICAL TRIALS	Sponsor:	Helixmith Co., Ltd.	
	Protocol Number:	VMALS-002-2b	
STATISTICAL ANALYSIS PLAN. PHASE 2-3-4			

- Incidence of treatment-emergent adverse events (TEAEs), treatment-emergent serious adverse events (TESAEs), and adverse events of special interest (AESIs) for Engensis compared to Placebo
- Incidence of clinically significant laboratory values for Engensis compared to Placebo

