6.14.1.4 Outputs planned for Adverse Events

TEAEs with start date and time before date and time of the Informed Consent for VMALS002-2B will be presented in a separate listing and will not be tabulated.

The following tables will be presented:

- Summary of TEAEs (Table 14.3.1.1)
- TEAEs by System Organ Class and Preferred Term (Table 14.3.1.2)
- TESAEs by System Organ Class and Preferred Term (Table 14.3.1.3)
- TEAEs by System Organ Class and Preferred Term and Maximum Severity (Table 14.3.1.4)

QMD Ref: Worldwide-TMP-ST-005-7.0 Effective: 12Aug2019	Governing QMD: Worldwide-SOP-ST-001
Confidentiality Statement	

This document is the property of Worldwide Clinical Trials Inc. and may not be duplicated, copied, altered or removed from company without prior approval from Worldwide Quality Assurance or in compliance with Worldwide Standard Operating Procedures.

Worldwide Clinical Trials Controlled Quality Management Document			
 WORLDWIDE CLINICAL TRIALS	Sponsor:	Helixmith Co., Ltd.	
	Protocol Number:	VMALS-002-2b	
STATISTICAL ANALYSIS PLAN. PHASE 2-3-4			

- TEAEs by System Organ Class and Preferred Term and Maximum Relationship (Table 14.3.1.5)
- TESAEs by System Organ Class and Preferred Term and Maximum Severity (Table 14.3.1.6)
- TESAEs by System Organ Class and Preferred Term and Maximum Relationship (Table 14.3.1.7)
- Incidence of Clinically Significant Laboratory Values (Table 14.3.1.8)
- AESIs by System Organ Class and Preferred Term (Table 14.3.1.9)

The following listings will be provided:

- All TEAEs (Listing 16.2.7.1)
- AESIs (Listing 16.2.7.2)
- TESAEs (Listing 16.2.7.3)
- TEAEs leading to study discontinuation (Listing 16.2.7.4)
- TEAEs related to study medication (Listing 16.2.7.5)
- TESAEs leading to death (Listing 16.2.7.6)
- AEs that registered as not TEAEs (Listing 16.2.7.7)

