6.14.2 Laboratory Data

Laboratory data consists of results of following examinations: serum chemistry, hematology and urine pregnancy test.

Serum chemistry will include the following variables:

- Sodium
- Potassium
- Chloride
- Bicarbonate
- Calcium
- Inorganic Phosphate
- Magnesium
- Glucose
- Amylase
- Lipase
- Lactate Dehydrogenase

QMD Ref: Worldwide-TMP-ST-005-7.0 Effective: 12Aug2019	Governing QMD: Worldwide-SOP-ST-001
Confidentiality Statement	

This document is the property of Worldwide Clinical Trials Inc. and may not be duplicated, copied, altered or removed from company without prior approval from Worldwide Quality Assurance or in compliance with Worldwide Standard Operating Procedures.

Worldwide Clinical Trials Controlled Quality Management Document			
 WORLDWIDE CLINICAL TRIALS	Sponsor:	Helixmith Co., Ltd.	
	Protocol Number:	VMALS-002-2b	
STATISTICAL ANALYSIS PLAN. PHASE 2-3-4			

- Blood Urea Nitrogen (BUN)
- Creatine Kinase (CK)
- Creatinine
- Aspartate Aminotransferase (AST)
- Alanine Aminotransferase (ALT)
- Alkaline Phosphatase
- Gamma-Glutamyl Transpeptidase (GGT)
- Total Bilirubin
- Total Protein
- Albumin

Hematology will include the following variables:

- White Blood Cells Count
- Hemoglobin
- Hematocrit
- Platelet Count
- Neutrophils Count

Serum chemistry and hematology analyses will be performed at Day 240 and Day 365. Measured values of serum chemistry and hematology analyses and their changes from baseline, will be presented with descriptive statistics at each visit by treatment group (Tables 14.3.4.1 and 14.3.4.3). Incidence of clinically significant values will be tabulated (Table 14.3.1.8), shift tables for abnormal values will be presented for each parameter (Tables 14.3.4.2, 14.3.4.4). Percentages for each parameter will be based on the number of participants who have at least one measurement for at baseline and at corresponding post-baseline visit.

Result of urine pregnancy test is variable with two possible values: positive / negative. The test should be performed only for women with childbearing potential at Day 365.

Results of serum chemistry, hematology and urine pregnancy tests will be listed (Listings 16.2.8.1 – 16.2.8.3).

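### SAP 6.2.13 does not exempt Table 14.3.1.8, so if that primary table is built from laboratory results it misses clinically significant values from unscheduled draws

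*SAP*

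**What the plan says.** SAP 6.2.13 sets a general rule for tables: "Only scheduled post-baseline values will be tabulated". It then adds "Post-baseline repeat / unscheduled assessments will not be tabulated", with those assessments going to listings. The only table named as an exception is Table 14.1.1.2, and that exception concerns combining Early Termination (ET) data with Day 365, not unscheduled data.

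SAP 3.1 gives as a primary endpoint "Incidence of clinically significant laboratory values for Engensis compared to Placebo". It is reported in Table 14.3.1.8, which the readable SAP text places in two sections:

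- SAP 6.14.2, directly after the Day 240 and Day 365 laboratory summaries: "Incidence of clinically significant values will be tabulated (Table 14.3.1.8").
- SAP 6.14.1.4, in the list of adverse event tables: "Incidence of Clinically Significant Laboratory Values (Table 14.3.1.8").

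Neither section says whether the table counts laboratory results or adverse event records, and neither lifts the 6.2.13 rule.

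On collection, footnote 5 to the Protocol 1.3 schedule says "Blood samples will be collected for serum chemistry and hematology assessments on Days 240 and 365/ET". Protocol 10.2.4 allows further testing when an event is followed up: "This may include additional laboratory tests or investigations". Protocol 1.1 (Overall Design) has assessment of clinically significant laboratory values run from the Day 180 Visit through to Day 365. Protocol 9.3.1 bases all safety summaries on available data.

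**The concern.** A scheduled-only rule is an ordinary convention for by-visit means and shift tables, where an extra draw has no visit row to sit in. An incidence endpoint is different: it asks whether a participant ever had a clinically significant value during follow-up. Applied to that question, the rule can turn a participant with an event into one without.

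Two programmers working from the readable text could also produce different counts for the same primary endpoint, one from laboratory results restricted to scheduled visits and the other from adverse event records. With at most 18 participants, a difference of one is visible in the reported percentage. At stake is the correctness of one primary table.

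**Working it through.** The plan has no figure of its own to reproduce here: the maximum of 18 is carried over from enrolment in VMALS-002-2 (SAP 4), and Protocol 9.3.1 specifies no formal testing. The check is mainly textual.

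**1. Does 6.2.13 reach Table 14.3.1.8?** The rule is unqualified and the table is not exempted. By contrast, SAP 6.2.2 expressly accepts unscheduled and repeat values for baseline, so the restriction applies after baseline only. ET values are kept, because 6.2.13 merges them with Day 365. Only unscheduled and repeat values drop out.

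**2. What happens under each possible source?**

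| Source of Table 14.3.1.8 | Value from a scheduled or ET draw | Only significant value from an unscheduled or repeat draw |
|---|---|---|
| Laboratory results | Counted | Not counted (6.2.13) |
| Adverse event records | Counted if recorded as an event | Counted if recorded as an event |

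The omission arises only in the first row. There it sits badly with Protocol 1.1, which has assessment continue throughout the extension, and with Protocol 9.3.1, which uses available data. SAP 9 nevertheless declares no change from the protocol analysis.

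**3. Can such draws occur?** Yes. Protocol 10.2.4 provides for extra tests in event follow-up. The scheduled draws have windows of ±7 days: Days 233–247 (15 days) and Days 358–372 (15 days). From Day 181 to Day 372 there are 372 − 181 + 1 = 192 days, so the windows cover 30/192 = 15.6%. On the other 162 days only an ET or unscheduled draw gives a value. This is a calendar count and says nothing about how often unscheduled draws happen or are abnormal.

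**4. What is the denominator?** The percentage sentence in SAP 6.14.2 requires a measurement at baseline and at the corresponding post-baseline visit. That is shift-table wording; SAP 6.14.5 uses nearly the same for its physical examination shift tables. The default in SAP 6.3 offers two bases, non-missing observations or the participant population. No single denominator for Table 14.3.1.8 follows.

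**5. Size of one omitted participant (100/n percentage points).**

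- Overall, at the maximum of 18: 100/18 = 5.6.
- Overall, if fewer enrol (assumed): 100/14 = 7.1; 100/10 = 10.0.
- Within an arm: the allocation is not given, so assumed sizes of 12, 9 and 6 give 100/12 = 8.3, 100/9 = 11.1 and 100/6 = 16.7.

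**The case against.** The strongest reply is that Table 14.3.1.8 may well be an adverse event table. Its number falls between 14.3.1.7 (TESAEs by relationship) and 14.3.1.9 (AESIs), whereas the laboratory summaries are numbered 14.3.4.1 to 14.3.4.4. Protocol 8.1.4 has clinically significant findings recorded as TEAEs, TESAEs or AESIs. On that reading 6.2.13 removes nothing. This stands: the adverse event source is as plausible as the laboratory source, so the omission is possible but not shown. SAP Section 11 is also blacked out, so the statement that no source is given covers the readable text only.

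It can also be said that the extra tests in Protocol 10.2.4 follow an event already reported. If that event was a significant scheduled value, the participant is already in the table. This also stands: the case that matters, where the only significant value is unscheduled, is narrower than all unscheduled draws.

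Three stronger readings are tempting, and the documents do not support them:

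- **A safety signal is lost.** The value is listed under 6.2.13 and should enter the TEAE tables through Protocol 8.1.4. Because findings are recorded there as a diagnosis, they may not be recognisable as laboratory values, but the event is not lost.
- **The undercount is likely.** The documents give no rate of significant values seen only at unscheduled draws, so any probability would rest on an assumed rate.
- **The definitions conflict, so the two sources must disagree.** Protocol 8.1.4 says "Clinically significant abnormal laboratory findings are those that are not associated with the underlying disease", while SAP 6.14.1.1 speaks of clinically significant findings that are associated with the disease and excludes them as TEAEs. The same exclusion stands in Protocol 10.2.1, and both sections also gloss clinically significant as unrelated to disease progression. The exclusion and Protocol 8.1.4 share an exception for findings more severe than expected. This is loose wording and does not establish different counts.

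**Conclusion.** The point holds conditionally. SAP 6.2.13 is unqualified, Table 14.3.1.8 reports a primary endpoint, and the readable SAP leaves open which records feed it. If laboratory results are used, a participant whose only clinically significant value came from an unscheduled or repeat draw is left out; if adverse event records are used, 6.2.13 has no effect.

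The consequence is limited to a possible undercount in one descriptive primary table: 5.6 points overall per omitted participant at 18, and 8.3 to 16.7 points within an arm at assumed sizes of 12 to 6. The frequency is unknown. No test or decision threshold depends on the count, and the event should still reach the companion TEAE endpoint. The correction is cheap and should be made because the endpoint is primary.

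**What to change.** Change the SAP text for Table 14.3.1.8 as follows:

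1. Name the data source.
2. Exempt the table from 6.2.13, and count each participant once if any post-baseline value in the extension (scheduled, unscheduled, repeat or ET) was judged clinically significant.
3. State one denominator, for example participants with at least one post-baseline draw in the extension, or the Safety Population. Either is defensible; the need is to choose.
4. Footnote, by arm, how many participants were counted through unscheduled draws only.

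The cost is two or three sentences and a small programming change. No new data are needed, since unscheduled values are already to be listed. The drawback is that unscheduled draws follow clinical need and may differ between participants; the footnote in item 4 lets the reader see this. The 6.2.13 rule can stay for by-visit summaries and shift tables.

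A minor change to the same section: label the pooled row Day 365/ET, as the Protocol 1.3 schedule does.

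Two ALSFRS-R items should be raised separately. First, SAP 6.2.9 totals items 1 to 9, whereas Protocol 8.2.1 describes twelve items scored 0 to 48; the two need reconciling. Second, the slope endpoint in SAP 3.2 is only plotted in SAP 6.15.1. Once the total is settled, add a descriptive slope difference with a 95% confidence interval. It will be imprecise: the half-width is t(16, 0.975) × √(1/n₁ + 1/n₂) × SD, where SD is the between-participant SD of slopes. That is 2.120 × √(2/9) = 1.00 SD at an assumed 9 and 9, and 2.120 × √(1/12 + 1/6) = 1.06 SD at an assumed 12 and 6.

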
 To determine whether IM administration of Engensis has positive effects on survival in ALS Participants 	
 Time to all-cause mortality compared to Placebo

 To evaluate Quality of Life improvement following Engensis injections in ALS Participants compared to Placebo 	
 Change from Baseline (Day 0) in Quality of Life (QoL) using the ALS Assessment Questionnaire (ALSAQ; with 40 items, ALSAQ 40) on Day 365 for Engensis compared to Placebo

 To evaluate Patient and Clinical Reported Outcome improvement following Engensis injections in ALS Participants compared to Placebo 	
 Patient Global Impression of Change (PGIC) and Clinical Global Impression of Change (CGIC) at Day 365 for Engensis compared to Placebo

Overall Design

VMALS-002-02b is a Phase 2a, 6-month extension study, multicenter study designed to assess the long-term safety of Engensis (containing the active pharmaceutical ingredient VM202) in Participants with ALS.

Participants will be enrolled in the VMALS-002-2b study following the completion of the Day 180 Visit of Study VMALS-002-2. Participants will continue to be identified by the same Participant number.

Assessments to be conducted during this VMALS-002-2b extension study are as follows: vital signs; weight and height; complete physical examination; a record of all concomitant medications and procedures; ALSFRS-R; Handheld Dynamometry (HHD); Slow Vital Capacity (SVC); Amyotrophic Lateral Sclerosis Assessment Questionnaire, 40 questions (ALSAQ-40); Patient Global Impression of Change (PGIC); Clinical Global Impression of Change (CGIC); and urine pregnancy test for females of childbearing potential. Assessments of TEAEs, TESAEs, AESIs, and clinically significant laboratory values will continue from the Day 180 Visit of Study VMALS-002-2 throughout the VMALS-002-2b extension study, to Day 365.

Study and Treatment Duration:

There will be no treatments during this extension study. The timing for visits in the VMALS-002-2b study starts at the conclusion of the Day 180 Visit in VMALS-002-2. Participants in VMALS-002-2b will be followed for 180 days to Day 365.

Visit Frequency:

Consented Participants will be seen and evaluated for safety at visits every 60 days (Days 240, 300, and 365/ET).

Intervention Groups and Duration:

[figure not shown]

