7. DISCONTINUATION OF STUDY INTERVENTION AND PARTICIPANT WITHDRAWAL

7.1. Participant Withdrawal/Discontinuation

Any Participant may voluntarily discontinue the study at any time without prejudice. The Investigator may discontinue a Participant from the study at any time if, in the Investigator's judgment, the Participant's health or safety would be compromised by remaining in the study.

Specific reasons for study discontinuation include the following:

- Participant decision
- Investigator's decision
- TEAEs or TESAEs
- Insufficient compliance with study requirements
- Lost to follow-up
- Other

The specific reasons for Participant discontinuation will be recorded in the eCRFs.

The following assessments will be performed at an Early Termination (ET) Visit, if possible, for Participants who discontinue prior to the Day 365 Visit.

- Complete Physical examination
- Vital signs, weight, height
- 12-lead ECG
- Serum chemistry and hematology
- Concomitant medications and procedures
- ALSFRS-R
- SVC
- HHD
- ALSAQ-40
- PGIC
- CGIC
- TEAEs, TESAEs, and AESIs

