10.3.2. Definitions

Active Infection	Chronic infection or severe active infection that may compromise the Participant's wellbeing or participation in the study, in the Investigator's judgment
Day 240, etc.	Day 240 (for example) refers specifically to the actual day of the Visit designated as the Day 240 Visit, and not to the 240 th day of the study for a Participant.
End of Study	Completion of the last Visit (Day 365) or procedures shown in the SoA for the last Participant remaining in the study
Highly Effective Contraception Method	See Contraceptive Guidance
Investigator	The PI or appropriate study site personnel whom the PI designates to perform a certain duty
Safety Analysis Population	All Participants in the study
Sponsor	Helixmith Co., Ltd. and its representatives contracted to provide services for study conduct
Participant	Anyone who is consented for the Safety Evaluation during VMALS-002-2b on or prior to Day 180 of VMALS-002-2
VM202	The active pharmaceutical ingredient of Engensis: a novel genomic complementary deoxyribonucleic acid (cDNA) hybrid human hepatocyte growth factor (HGF) coding sequence (HGF-X7) expressing two isoforms of HGF, HGF ₇₂₈ and HGF ₇₂₃

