3.2 Exploratory Endpoints

- Change from Baseline (Study VMALS-002-2 Day 0) in total mean Revised Amyotrophic Lateral Sclerosis Function Rating (ALSFRS-R) scores at Day 365 for Engensis compared to Placebo
- Change from Baseline (Study VMALS-002-2 Day 0) in ALSFRS-R subscores for Fine and Gross Motor Functions (sum of scores for items 4 to 9) and for Bulbar Function (sum of scores for items 1 to 3) at Day 365 for Engensis compared to Placebo
- Changes in the slope of the total ALSFRS-R score over time for Engensis compared to Placebo
- Change from Baseline (Study VMALS-002-2 Day 0) in muscle strength assessed bilaterally by Handheld Dynamometry (HHD) in muscles in the upper and lower extremities at Day 365 for Engensis compared to Placebo
- Change from Baseline (Study VMALS-002-2 Day 0) in Quality of Life (QoL) using the ALS Assessment Questionnaire (ALSAQ; with 40 items, ALSAQ 40) on Day 365 for Engensis compared to Placebo
- Patient Global Impression of Change (PGIC) and Clinical Global Impression of Change (CGIC) at Day 365 for Engensis compared to Placebo
- Change from Baseline (Study VMALS-002-2 Day 0) in Slow Vital Capacity (SVC) at Day 365 for Engensis compared to Placebo
- Time to tracheostomy for Engensis
- Time to all-cause mortality compared to Placebo

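### SAP 6.2.13 tabulates every Early Termination value with Day 365, whatever day it was taken, so Day 365 results can mix values from about Day 181 to Day 372

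*SAP*

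**What the plan says.** SAP 6.2.13 states that "data of the Early Termination visit will be combined with data of Day 365 visit". The rule covers all tables except the participant-visit table (14.1.1.2). It names no minimum day, analysis window or nearest-visit mapping, and neither document plans a table without ET values.

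Protocol 7.1 sets out who has such a visit: "The following assessments will be performed at an Early Termination (ET) Visit, if possible, for Participants who discontinue prior to the Day 365 Visit". The list includes ALSFRS-R, SVC, HHD, ALSAQ-40, PGIC, CGIC, laboratory tests, vital signs, ECG and physical examination. The same section allows departure at any point: "Any Participant may voluntarily discontinue the study at any time without prejudice". Protocol 1.1 fixes the start of follow-up: "The timing for visits in the VMALS-002-2b study starts at the conclusion of the Day 180 Visit in VMALS-002-2".

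The exploratory endpoints in SAP 3.2 are tied to one time point. The ALSFRS-R total, for example, is compared as "scores at Day 365 for Engensis compared to Placebo", and subscores, HHD, SVC and ALSAQ-40 follow the same pattern. The Schedule of Activities (Protocol 1.3) gives the Day 365 visit a window of ±7 days and shares one column between Day 365 and ET. SAP 6.15.1 to 6.15.5 summarise these outcomes descriptively by visit, and SAP 6.3 adds 95% confidence limits for mean changes from baseline.

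**The concern.** A participant who withdraws alive soon after Day 180 and attends an ET visit has six-month values tabulated with the one-year values. Nothing goes to Day 240, even if that is the nearer visit.

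ALS is progressive (Protocol 2.2.1), so on function, strength, vital capacity and quality of life the early value shows less decline than that person would be expected to have by Day 365. With at most 18 participants in both arms together, one or two such values can move an arm mean. If the arms differ in the number or timing of ET visits, part of the apparent arm difference is a difference in follow-up time.

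The Day 365 laboratory, vital-sign, ECG and physical-examination tables, and the Day 365 PGIC/CGIC tables, also mix observation times of roughly 6 to 12 months, although long-term safety is the primary objective. None of these summaries uses the actual assessment date, so the analysis does not correct for the mixture.

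**Working it through.** The plan has no figure of its own to reproduce: the documents give no decline rate, SD, dropout rate or arm split.

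**Timing, from the documents.** ET visits can fall from just after the Day 180 Visit (about Day 181), and the Day 365 window closes at 365 + 7 = Day 372. The share of the year not yet observed at an ET visit on day d is (365 − d)/365:
- Day 181: 184/365 = 50.4%
- Day 240: 125/365 = 34.2%
- Day 300: 65/365 = 17.8%

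**Size, under assumptions.** Assume linear decline of s points per month, the same for everyone, with k ET participants among n in an arm.

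- True mean decline at one year = s × 365/30.4375, which is 11.99 points at s = 1.
- Understatement after pooling = (k/n) × s × (365 − d)/30.4375.
- As a share of the true decline this is (k/n) × (365 − d)/365, which does not depend on s.

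Results for s = 1 and n = 9:

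| ET day | k = 1 | k = 2 | k = 3 |
|---|---|---|---|
| 181 | 0.67 (5.6%) | 1.34 (11.2%) | 2.02 (16.8%) |
| 240 | 0.46 (3.8%) | 0.91 (7.6%) | 1.37 (11.4%) |
| 300 | 0.24 (2.0%) | 0.47 (4.0%) | 0.71 (5.9%) |

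Over s = 0.5 to 1.5 the same grid runs from 0.12 to 3.02 points. With s = 1 and two ET visits at Day 181, the shift is 2.02 points in an arm of 6 and 1.01 in an arm of 12. If only one arm has ET visits, the whole shift appears as an arm difference.

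**Unequal rates.** Let ET participants decline f times as fast as completers (s = 1, n = 9, k = 2). The pooled mean shows more decline than completers alone once f × d > 365, that is f > 365/d: 2.02 at Day 181, 1.52 at Day 240 and 1.22 at Day 300.

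- f = 1, ET at Day 181: true 11.99, pooled 10.65, completers only 11.99.
- f = 2, ET at Day 181: true 14.66, pooled 11.97, completers only 11.99.
- f = 2, ET at Day 300: true (7 × 11.99 + 2 × 2 × 11.99)/9 = 14.66; pooled (7 × 11.99 + 2 × 2 × 9.86)/9 = 13.71; completers only 11.99.

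For f from 1 to 3 and these three ET days, pooling falls short of the true one-year decline by 0.47 to 4.03 points. A completers-only mean is exact at f = 1 but is further off than pooling once f exceeds 365/d.

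**The case against.** The strongest point against a change is that removing ET values can make matters worse. If those who leave decline faster, a Day 365-only mean is close to a completers-only mean. In the f = 2, Day 300 case pooling errs by about 1.0 point and the completers-only mean by about 2.7. This stands. It is the reason to keep the pooled row as a sensitivity and to add an analysis on actual study day.

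Second, days in this protocol are nominal labels. Protocol 10.3.2 says a day such as Day 240 "refers specifically to the actual day of the Visit designated as the Day 240 Visit" and rules out reading it as an elapsed-day count. The schedule also has one shared Day 365/ET column. That explains the SAP's practice, but the column sets which assessments are done. No protocol text says that ET values are analysed as Day 365 values. The list of tables is not visible, so the column labels cannot be checked.

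Third, living withdrawal may be rare. In the sponsor's Phase 1/2 ALS study (Protocol 2.2.6.1), 17 of 18 participants completed nine months and the other died. ET visits also take place only if possible. Both points are fair, though that study had a different design and nine months is shorter than one year.

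Fourth, the functional tables are exploratory and descriptive. All data are listed, and Listing 16.2.1.1 gives discontinuation and last-visit dates. This limits the consequence, but the tabulated means and limits would still carry the wrong time.

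A reader might infer that the rule always flatters the one-year result, or favours Engensis. The documents do not support either. The sign depends on the comparator, and nothing shows which arm would have more or earlier ET visits.

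**Conclusion.** The concern holds as a problem of timing and labelling. Followed as written, the plan gives Day 365 results that can include values about six months early, and no stated rule or sensitivity table lets the reader separate them.

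For progressive measures, the pooled value shows less decline than the ET participant's own expected Day 365 state. Under equal linear decline and one to three ET visits in an arm of nine, that is 2.0% to 16.8% of the mean one-year decline. Decline rate, arm split, and the number and timing of ET visits are all assumptions. The point figures are illustrative only: SAP 6.2.9 sums ALSFRS-R items 1 to 9, whereas Protocol 8.2.1 describes a twelve-item score, so the rate per month depends on which total is used. The percentages do not depend on the rate.

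The damage is confined to by-visit tables. Adverse-event incidence does not depend on the visit label, and the times to tracheostomy and death use actual dates. SAP 6.2.13 names tables only and does not say how ET values enter the ALSFRS-R slope figure. It would be too strong to say that the primary adverse-event results are compromised.

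**What to change.** Replace the last sentence of SAP 6.2.13 with wording to this effect: *In by-visit tables, the Day 365 row contains only assessments from the Day 365 visit and ET assessments within its ±7-day window. All other ET assessments are shown on a separate Early Termination row with n and the median and range of study day. A pooled Day 365/ET row is given as a labelled sensitivity.*

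If ET values are also assigned to a nearer visit, state the slot bounds and use only visits at which that assessment is scheduled. For laboratory tests, ECG, physical examination, ALSAQ-40 and PGIC/CGIC these are Days 240 and 365; a Day 300 slot would create a visit that the schedule does not contain. Say which day count the bounds use, since SAP 6.2.3 numbers the first injection day as 1 while the protocol calls it Day 0.

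For ALSFRS-R, HHD and SVC, add a summary on actual study day, such as individual slopes or a mixed model, because a Day 365-only mean does not remove bias from dropout. State how ET values enter the slope figure in SAP 6.15.1.

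The cost is a short SAP edit and some programming before database lock, a smaller n on the Day 365 row, and a few more table rows. No data are lost and no visits change.
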